After meeting full criteria and consenting to participate in the study participants will be asked to complete 4 psychosocial interviews. Because the inclusion criteria for this study requires that the participants be Spanish speakers, all participants will be assessed in Spanish by Spanish speaking research staff. Participants complete inperson assessments at baseline (T1) and at approximately (plus or minus 2 months) 3-months (T2), 6- (T3) & 12months (T4) post baseline. The interviews may vary in length and may take up to 2.5 hours to complete, depending on the ability of the participants to answer each question. Participants will have the choice of visiting our study office or conduct the interview at their home or via Zoom or phone if they are not able to meet us in-person. Participants will also be asked at baseline to complete a technology-based questionnaire; this questionnaire will allow research staff to determine the best method to deliver study-related material related to the group sessions. The study-related material will consist of audio files covering relaxation techniques reviewed throughout their 10-week participation. All assessments are completed and scored via RedCap, an online research management tool that enables researchers to create study websites for securely capturing data. RedCap is a web-based system led by the Department of Medical Social Sciences. [name] the PI has extensive experience working with this system. All screening and assessment instruments are guided by our conceptual model for managing PC, have excellent psychometric properties (e.g., Cronbach's $\alpha \ge .70$) and have been translated and validated in Spanish speaking populations.

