Participants will be randomized by cluster randomization (C-CBSM or CBSM) to balance treatment type across conditions. We project to retain 140 participants at our 12-months post-intervention assessment visit (T4). All participants will be asked to participate in 10-weekly 90-minute in person sessions targeting CBT based skills for managing stress and self-management in one of two experimental conditions—a linguistically translated (Spanish) and culturally adapted cognitive behavioral stress and self-management (CBSM) condition (i.e., C-CBSM) or in a standard version of CBSM that is only linguistically translated (CBSM). Following the baseline visit (T1, pre C-CBSM or CBSM), participants are randomly assigned into one of our experimental or control condition groups.

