Experimental Design. Our primary aim is to examine the effectiveness and incremental efficacy of a 10-week group-based, linguistically and culturally adapted cognitive behavioral stress and self- management intervention (C-CBSM) vs. a linguistically translated standard CBSM (no cultural adaptation) on symptom burden and HRQOL in Hispanic men treated for localized PC. This is randomized control trial (RCT) with a 2x4 design with group assignment (C-CBSM vs. CBSM) as the between-group factor and time (baseline [T1], post-intervention [T2], 6-mos. [T3] & 12-mos [T4]. Post intervention [T4]) as the within-group factor. Primary outcomes are symptom burden (i.e., urinary & sexual function) and HRQoL (e.g., physical, social, emotional & functional). We will make every effort to engage and promote participation in all 10 sessions however we anticipate that some cases will not be able to attend all sessions due to multiple circumstances, such as change in employment or work schedule, health issues, relocation, unforeseen transportation difficulties, family crisis, social/environmental/health crisis (COVID-19), etc. This study uses an intent to treat intervention design model thus participation in all sessions may differ for some individuals. We estimate attrition at ~22% over the study although our prior rate is closer to 10%. Cluster randomization will occur by group type (C-CBSM vs. CBSM).

Experimental Conditions:

CBSM. The standard English language^{59,60} intervention was developed for stress management, risk reduction, health maintenance and self-management by providing relaxation training and CBT-based strategies to improve symptom management, interpersonal adjustment and HRQoL, and reduce arousal and negative mood in men treated for PC. This standard, not culturally-adapted CBSM underwent forward and backward translation by Action Translation Services¹⁷² with internal verification.

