Hypothesis 2 (Aim 2): C-CBSM will show significantly greater improvements in intervention targets (i.e., improved stress management, and reduced psychological distress and interpersonal disruption) from baseline (T1) to 3-, 6- and 12-month follow-ups (T2-T4) relative to CBSM.

Test of Study Hypotheses. All analyses will be intent-to-treat analyses ¹⁹⁸ and linear mixed models will be used to test Hypotheses 1-2. These models classify time of measurement as a categorical variable in order to give full flexibility to different mean time courses in the two randomized groups. Latent growth modeling (LGM)¹⁸⁵ with relevant covariates is used to test the three sub-hypotheses of Aim 4. Advances in LGM and structural equations modeling (SEM)¹⁸⁶ allow us to blend these methods to test complex models of change¹⁸⁷ as latent growth models. LGM allows for missing data, as well as irregularly spaced measurements across time, time-varying and invariant covariates, accommodation of individual-specific deviations from the mean time trend and estimation of population variance associated with individual effects. Analyses of the first 3 hypotheses inform the functional form of the LGM time course. Software to implement these analyses is available (e.g. Mplus). ^{188,189} The software permits the blending of continuous and categorical data, the specification of linear and nonlinear models of change, and the specification of longitudinal structural models. Adequate model fit will be established by several fit indicators (Comparative Fit Index [CFI] > .95, Root-Mean-Square Error of Approximation [RMSEA] ≤ .05, Standardized Root-Mean-Square Residual [SRMR] < .08). ¹⁹⁰

Exploratory Hypotheses:

Hypothesis 3 (Aim 3): C-CBSM will show significantly greater activation of leukocyte glucocorticoid receptor (i.e., greater sensitivity) and lower inflammatory gene expression (i.e., less activation) pathways from baseline (T1) to 3-, 6- and 12-month follow-ups (T2-T4) relative to CBSM.

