To Test Exploratory Hypotheses. Aim 3: For Hypotheses 3, the linear mixed model will include fixed effects for the experimental group (C-CBSM vs. CBSM) and observation time (T1-T4), and random effect for person with a compound symmetry covariance structure for the repeated residuals within person. A group by time interaction and post-hoc tests on this model effect will indicate whether and how the time course of the dependent variable differs between the groups. Hypotheses 1-3 will all be analyzed in a similar manner using the outcome measures described in sections C.6.c (Primary Outcomes), C.6.d (Intervention Targets) and C.6.e (Inflammation) respectively. These measures include markers of symptom burden, systemic inflammation, and cytokine production following cellular activation with TLR ligands. Data from gene expression profiling are analyzed using advanced bioinformatics techniques, and described in C.6.e, and as reported previously by Antoni et al.¹²⁴ As each outcome across the different study hypotheses have been carefully selected to address a priori hypotheses, no adjustment for testing of multiple outcomes will be made. However, within the analysis of a specific outcome, Tukey or Bonferroni adjustment will be made for the multiple tests across different time points. The power calculation below adjusts for this multiplicity. Aims 4a-4c: These hypotheses involve tests of proposed mediators of C-CBSM's effect on our primary outcomes. To test mediation with LGM, individual change trajectory (in each outcome of interest) is characterized by an intercept and a slope factor. The overall pattern of change (e.g., linear, quadratic, etc., as informed by analyses for Aims 1-3) for the whole group can be specified by a particular set of coefficients associated with the slope factor. First, we will specify a growth curve model for all participants with an intercept factor representing our outcome of interest at baseline, and the slope factor reflecting the change trajectory in our outcome measure from T1 to T4. For example, to test that increased stress management skills (e.g., MOCS) in the C-CBSM group accounts for reductions in symptom burden (e.g., EPIC-S), we will first test a LGM model without the stress management skills (the mediator) and then test the model with change in stress management skills from T1 to T4. In the model without the stress management skills, we expect that group assignment is not related to baseline symptom burden, but that group assignment will be related to a greater negative change (reduction) in symptom burden scores. In the next step, we will add stress management skills and expect that after adding this mediator in the model, the path between group assignment and symptom burden slope will become non-significant, while the path between the mediator and symptom burden slope is significant thus suggesting mediation. This approach will be applied to test all mediation models in hypotheses 4a-4c. 191,192 Aim 5a-5b: To evaluate moderators and mechanistic pathways of C-CBSM's effects, we will use LMM and latent variable mediation models. For Hypothesis 5a, we will test moderation by including interaction terms between group assignment (C-CBSM vs. CBSM) and each moderator of interest (e.g., SES, acculturation, Hispanic ancestry, treatment type) within the LMM framework. These models will include fixed effects for group, time (T1-T4), the moderator, and the group × moderator and group × time × moderator interactions. A significant three-way interaction (group × time × moderator) will indicate that change in the outcome (e.g., inflammation, symptom burden, HRQoL) over time differs by both treatment group and the level of the moderator. Post-hoc comparisons will clarify the nature of the moderation effects across timepoints. For Hypothesis 5b, we will test whether improvements in cardiometabolic markers (e.g., lipids, fasting glucose, blood pressure) in the C-CBSM group are mediated by reductions in inflammation using SEM. Parallel process LGMs will estimate trajectories for inflammatory markers and cardiometabolic outcomes across time. The indirect effect from group assignment to cardiometabolic outcome slope via inflammation slope will be tested. This approach allows for simultaneous modeling of changes over time, capturing both within- and between-subject effects. Model fit will be evaluated using standard criteria (CFI > .95, RMSEA ≤ .05, SRMR < .08), and significance of indirect effects will be tested using bias-corrected bootstrapped confidence intervals.

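### The mixed model leaves arm means free at the pre-randomisation visit and gives all visit pairs one correlation, which wastes 12-month precision and puts the 12-month error rate at risk

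*Combined protocol and SAP*

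**What the plan says.** The section To Test Exploratory Hypotheses sets out the model for Hypothesis 3. It has fixed effects for arm and visit (T1 to T4), a "random effect for person with a compound symmetry covariance structure for the repeated residuals within person", and a group-by-time test followed by post-hoc tests. The same section adds that "Hypotheses 1-3 will all be analyzed in a similar manner using the outcome measures described", which brings in the primary aim. Test of Study Hypotheses treats time as categorical in order to "give full flexibility to different mean time courses in the two randomized groups". T1 is therefore a response visit with its own mean in each arm.

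Three other statements bear on this:

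- Randomization Protocol: "Following the baseline visit (T1, pre C-CBSM or CBSM), participants are randomly assigned".
- The mediation text for Aims 4a-4c: "we expect that group assignment is not related to baseline symptom burden".
- Assessment and Data collection: visits at baseline and at "3-months (T2), 6- (T3) & 12months (T4) post baseline".

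On sample size at T4, Randomization Protocol says "We project to retain 140 participants" and Experimental Design says "We estimate attrition at ~22% over the study". For Hypotheses 1-3 no baseline-outcome adjustment, other covariance structure, robust standard error or sensitivity analysis is stated.

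**The concern.** There are two separate issues.

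**Precision.** T1 is measured before assignment, so the arms have the same expected T1 mean. Leaving the T1 means free makes the group-by-time contrast a comparison of change scores. That comparison is unbiased, but it ignores a known equality and so has a larger variance than necessary. This holds whether or not the correlation decays.

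**Error rate at T4.** A person effect plus compound symmetry implies one correlation for all six visit pairs, so the model gives the changes T2-T1, T3-T1 and T4-T1 the same variance. If scores 12 months apart correlate less than scores 3 months apart, the T4 standard error is too small and the T2 standard error too large. The visit-specific conclusion is what could mislead, above all on whether benefit lasts to 12 months.

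A secondary matter is covariate choice. Covariates enter by a p<.10 screen on the trial's own data, so the set can differ between outcomes. Treatment type, which the randomisation is said to balance, is not a fixed term in the model.

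**Working it through.** **Inputs from the documents.** Effect sizes 0.40 (5%) and 0.49 (1%), two-sided, in SDs of change, with 100 per arm (Power Analyses); 140 men at T4, or 70 per arm; about 22% attrition, or 78 per arm; visits at 0, 3, 6 and 12 months.

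**Assumed, because the documents give no correlations.** Equal variances and four patterns: constant 0.65; linear decay from 0.70 to 0.60, or from 0.75 to 0.55, between lags of 3 and 12 months; and 0.8 per 3 months (0.80, 0.64, 0.512, 0.4096 at lags 3, 6, 9, 12).

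**1. The plan's own figure.** Power = Φ(d√(n/2) − z).
- d = 0.40, n = 100, 5%: Φ(2.828 − 1.960) = Φ(0.868) = 80.7%.
- d = 0.49, n = 100, 1%: Φ(3.465 − 2.576) = Φ(0.889) = 81.3%.

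The stated 80% reproduces as the power of a plain change-score test. No credit is taken for baseline information.

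**2. Common T1 mean, complete data.** With variance σ² at each visit and T1-T4 correlation ρ, the per-person variance of the T4 contrast falls from 2σ²(1−ρ) to σ²(1−ρ²), a ratio of (1+ρ)/2. The standardised effect is multiplied by √(2/(1+ρ)). At ρ = 0.5, 0.40 becomes 0.462 and power is Φ(3.266 − 1.960) = 90.4%. At ρ = 0.7 it becomes 0.434 and power is 86.6%.

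**3. With dropout at T4.** Generalised least squares with 100 per arm at T1-T3, fewer at T4, and the covariance correctly specified in both models. T4 power, free to common T1 mean:

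| Pattern | 70 per arm, 0.40, 5% | 78 per arm, 0.40, 5% | 70 per arm, 0.49, 1% |
|---|---|---|---|
| constant 0.65 | 71% to 77% | 74% to 81% | 69% to 77% |
| 0.70 to 0.60 | 71% to 78% | 74% to 82% | 70% to 79% |
| 0.75 to 0.55 | 72% to 80% | 75% to 83% | 70% to 81% |
| 0.8 per 3 months | 73% to 84% | 75% to 87% | 72% to 85% |

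At 70 per arm the gain equals 16% to 32% more information. Simulation with an estimated unstructured covariance (0.75 to 0.55, 70 at T4, 1,000 trials per setting) gave power of 72.5% free and 80.8% common, with type I error of 5.1% and 4.8%.

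**4. Error under compound symmetry.** The model gives every change the variance 2(1 − r̄), where r̄ is the mean of the six correlations. The true variance for visit j is 2(1 − r₁ⱼ). So model SE / true SE = √[(1 − r̄)/(1 − r₁ⱼ)], and the true error is 2[1 − Φ(z × ratio)].

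| | 0.70 to 0.60 | 0.75 to 0.55 | 0.8 per 3 months |
|---|---|---|---|
| r̄ | 0.661 | 0.672 | 0.634 |
| r₁₄ | 0.60 | 0.55 | 0.410 |
| T4 SE ratio | 0.92 | 0.85 | 0.79 |
| T4 error, nominal 5% | 7.1% | 9.4% | 12.3% |
| T2 error, nominal 5% | 3.7% | 2.5% | 0.8% |
| T4 error, Bonferroni 1.67% | 2.8% | 4.1% | 5.9% |
| Any Bonferroni rejection, T2-T4 | 4.7% | 5.5% | 6.9% |
| Interaction test | 5.1% | 5.5% | 6.4% |

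The last two rows come from 40,000 simulated trials per pattern (70 per arm, complete data). The any-rejection figure is 4.3% when compound symmetry is true and about 4.2% with an unstructured covariance.

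**5. Both changes are needed.** A common T1 mean with compound symmetry kept still gives 7.8% at T4 for decay from 0.70 to 0.50, and 10.7% for 0.80 to 0.40 (100 per arm, complete). An unstructured covariance with free T1 means corrects the error but leaves power at the planned 80.7%.

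**The case against.** The case against has real content.

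- **The planned contrast is not wrong.** It estimates the difference in mean change, which is what the power section uses. This stands: the first issue is lost efficiency, not bias.
- **The gain could be smaller.** At 70 per arm, a constant correlation of 0.80 gives 70.5% to 74.0% and 0.85 gives 70.5% to 73.1%. A constant 0.65 with the T1 SD at 0.8 of later SDs gives about 69% to 70%. This stands as a lower range of 1 to 4 points.
- **The two harms do not add.** Under the three decay patterns, the planned model's own T4 rejection rates are 76% / 81% / 85%, against 78% / 80% / 84% after the fix. This is correct, but the planned rates are bought with inflated type I error.
- **Multiplicity control limits the damage.** If post-hoc tests follow only a significant interaction and use Bonferroni, simulated error is 3.2% / 3.7% / 5.3% for any false claim and 1.9% / 2.9% / 4.8% for a false T4 claim. The family of visits is therefore little affected. The T4 figures still exceed the 1.67% allotted to one visit.
- **Other models exist.** The Aim 4 growth models allow individual slopes, but they test mediation and do not replace the tests of Hypotheses 1-3.
- **Scope rests on one sentence.** The covariance is written for Hypothesis 3. That sentence is nevertheless the only specification Hypotheses 1 and 2 have.
- **Timing varies.** Other sections place T4 at 12 months after the intervention, and visit windows are plus or minus 2 months. A later T4 widens the spacing and makes a single correlation harder to defend.
- **Clustering is ignored.** Men are randomised by cluster and treated in groups, so the absolute powers above should not be read as the trial's power.

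**Conclusion.** The concern holds. The plan gives up T4 precision that its own baseline data would supply. At 70 per arm and 0.40 SD the gain is about 6 to 11 points of power over the assumed patterns, falling to 1 to 4 points if correlations are very high or the T1 spread is narrow. This part needs only that assignment follows T1, as the protocol states.

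The T4 error is conditional. It is nil if all visit pairs share one correlation and variance, and 7.1% to 12.3% for an unadjusted 5% test under the three decay patterns. Error across visits together moves much less. With unequal variances the direction can reverse: a T1 SD of 0.8 with constant correlation 0.6 makes the planned T4 test slightly conservative (4.1%, 100 per arm, complete data). That is a further reason not to fix the covariance shape in advance. This is an improvement that should be made, not a flaw that invalidates the analysis.

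**What to change.** For Hypotheses 1-3, state the model in full:

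- responses at T1 to T4, with fixed effects for time and for group-by-time at T2, T3 and T4 only, so that the T1 mean is common; or, equivalently in purpose, follow-up scores adjusted for the T1 score;
- an unstructured 4×4 within-person covariance in place of the person effect and compound symmetry;
- REML with Kenward-Roger degrees of freedom, which uses the same available data as the planned full-information likelihood;
- the Tukey or Bonferroni adjustment across visits kept as planned.

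As a secondary change, replace the p<.10 screen with a covariate list fixed before outcome data are examined, the same for every outcome and including treatment type. A term for the therapy group is a separate addition to this model. The common T1 mean and unstructured covariance do not deal with clustering.

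The cost is SAP wording and ten covariance parameters for about 200 men. No visits, data or participants are added.

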
Additional Retention Strategies: Participants who may be experiencing multiple challenges (e.g., financial, access to care, comorbid illness, etc.) present special problems for which alternative procedures are required in order to maximize retention. As mentioned above we will be compensating participants for their assessment visits, and mailing them follow-up reminder cards two to three weeks before their subsequent appointments. If a participant does not call to make an appointment for re- assessment, the contact staff will call on the individual indicated as primary contact by the participant. This contact may take place through telephone or face-to-face. The staff person making the call will attempt to collect information that will lead to location of the participant. Secondary and tertiary contacts named in the participant's locator files will also be part of the contact staff's repertoire for finding a seemingly lost participant. In the event that cancer or other medical condition hinders a participant's ability to attend an assessment visit, we will offer them the option of home visits for data collection. In all such cases, we will respect the participants' right to refuse this option and will be acutely sensitive to their desire to maintain their privacy during these difficult times. If the participant does consent to home visits, we will furnish the personnel to visit them. If the full battery of tests is too burdensome, we will use an abbreviated battery consisting of our primary outcome measures. For participants who refuse to return for assessments or who have dropped out of the study, we will offer them the opportunity to schedule their assessment at any time of day at the most convenient location and will offer them the opportunity to complete only the abbreviated form of the battery should they so request. We will also respect a participant's refusal to undergo blood draws. Repeated failure to locate a participant for follow-up will lead to our contacting the Florida Departments of Health to learn of death certificates issued in the period since the missed assessment.

Data Analysis Plan including Statistical Procedures Study Hypotheses:

Hypothesis 1 (Aim 1): C-CBSM will show significantly greater reduced symptom burden and improved HRQoL from baseline (T1) to 3-, 6- and 12-month follow-ups (T2-T4) relative to CBSM.

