
Preliminary Analyses and other Statistical Considerations. Descriptive statistics will be computed to ensure values are within expected ranges and to eliminate any errors. We will use PRELIS2^{193,194} to examine multivariate normality. Non-normally distributed variables will be transformed using log transformations. We will compute estimates of internal consistency (Chronbach's α) for all scales and composite scores. If reliability is <.70, we will evaluate the internal consistency of the measure and delete items or subscales as needed.¹⁹⁵

Power Analyses. The primary aim compares pre-post change in symptom burden scores between the randomized arms. A sample of 100 per arm is assumed, although T1-T3 time points will have larger samples. Power is based on the effect size defined as the group difference in the mean change divided by the standard deviation of the change. Power calculations are based on effects of the C-CBSM pilot study. With 100 per arm, there is 80% power to detect an effect size of 0.40 assuming a two-tailed test and a Type I error rate of 5%. Since multiple tests look at change in various post-intervention time points, using a Type I error rate of 1% results in a detectable effect size of 0.49. If effect sizes are calculated from Figure 6 from our preliminary work, then the observed effect sizes as defined above are 0.52 for FACT-G and 0.40 for EPIC-S. Effect sizes for subscales FACT-PWB and FACT-EWB are

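### The time-point adjustment is left as Tukey or Bonferroni over an unstated family, and the 1% planning level is stricter than the three Hypothesis 1 contrasts need: name the three contrasts and test them with Holm

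*Combined protocol and SAP*

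**What the plan says.** Hypothesis 1, under Study Hypotheses, concerns improvement "from baseline (T1) to 3-, 6- and 12-month follow-ups (T2-T4) relative to CBSM". That is three between-arm contrasts of change from baseline for each outcome.

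The analysis is described under To Test Exploratory Hypotheses, which also covers the primary aim: "Hypotheses 1-3 will all be analyzed in a similar manner". The model is a linear mixed model with a "random effect for person with a compound symmetry covariance structure for the repeated residuals within person". The testing sequence is given as "A group by time interaction and post-hoc tests on this model effect will indicate whether and how the time course" differs between the groups. Within one outcome, "Tukey or Bonferroni adjustment will be made for the multiple tests across different time points". No adjustment is made across outcomes, and the power calculation is said to allow for the time-point multiplicity.

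The Power Analyses section assumes 100 per arm and defines the effect size as the arm difference in mean change divided by the SD of change. It gives 80% power for 0.40 at two-sided 5%. Because change is tested at several post-intervention time points, it adds that "using a Type I error rate of 1% results in a detectable effect size of 0.49". The pilot effects it cites are 0.52 for FACT-G and 0.40 for EPIC-S. The Randomization Protocol section projects 140 men retained at T4.

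**The concern.** The hypothesis and the power text both point to three baseline-referenced contrasts, but the rule that decides whether each is significant is not fixed. The plan offers two methods and no list of comparisons. Bonferroni over three contrasts fits the wording, and so does Tukey over all pairs of visits. The second would also pay for comparisons among T2, T3 and T4, which Hypothesis 1 does not make. The choice could be made after the p-values are seen.

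The only number attached to the adjustment is the 1% used for planning, and it is stricter than three contrasts require. The pilot EPIC-S effect of 0.40 lies below the plan's own adjusted detectable effect of 0.49, so the strictness of the visit-level test matters for symptom burden.

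**Working it through.** **Inputs.** From the plan: 100 per arm, two-sided tests, 80% power, effects of 0.40 and 0.52 in SD of change, compound symmetry, 140 retained at T4. Assumed: men are independent, and 140 splits into 70 per arm. Under compound symmetry, two changes sharing a baseline have variance 2σ²(1−ρ) and covariance σ²(1−ρ), so the three contrasts correlate at 0.5.

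**1. The plan's figures.** Detectable effect d = (z₁₋α/₂ + z₀.₈₀)·√(2/n), with √(2/100) = 0.1414.
- 5%: (1.960 + 0.842) × 0.1414 = 0.396 (t-test 0.398). Stated 0.40.
- 1%: (2.576 + 0.842) × 0.1414 = 0.483 (t-test 0.487). Stated 0.49.

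Both reproduce.

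**2. Per-test levels that the wording allows.**
- Bonferroni over three contrasts: 0.05/3 = 0.0167.
- Tukey over all six pairs of four visits: cut-off q/√2 = 2.569, level 0.0102.
- Tukey over all eight group-by-time cells (28 pairs): level 0.0024.

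The planned 1% is close to the second and also equals 0.05/5. The documents do not say how it was chosen.

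**3. Family-wise error over the three contrasts (correlation 0.5).** Unadjusted 12.5%; at 0.0167, 4.4%; at 1%, 2.7%. Some adjustment is needed if any visit can count as a success, but 1% leaves almost half of the 5% unused.

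**4. Power for one visit's contrast.** Power ≈ Φ(d·√(n/2) − z₁₋α/₂).
- n = 100, d = 0.40: 0.40 × √50 = 2.828. At 1%, Φ(2.828 − 2.576) = 60.0%. At 0.05/3, Φ(2.828 − 2.394) = 66.8%.
- n = 70, d = 0.40: 0.40 × √35 = 2.366. At 1%, Φ(2.366 − 2.576) = 41.7%. At 0.05/3, Φ(2.366 − 2.394) = 48.9%.
- n = 100, d = 0.52: 0.52 × √50 = 3.677. At 1%, 86.5%. At 0.05/3, 90.0%.

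Holm compares the ordered p-values with 0.05/3, 0.05/2 and 0.05. Its power comes from 600,000 simulated draws of three correlated z statistics.

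| Per arm, effect | 1% | Bonferroni, 3 | Holm, effect at T4 only | Holm, equal at all visits |
|---|---|---|---|---|
| 100, 0.40 SD | 60.0% | 66.8% | 66.9% | 74.5% |
| 70, 0.40 SD | 41.7% | 48.9% | 49.0% | 56.1% |
| 100, 0.52 SD | 86.5% | 90.0% | 90.2% | 94.3% |

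Tukey over six pairs gives practically the 1% column. Tukey over 28 pairs would give 42.0% at 100 per arm and 0.40 SD.

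**5. Splitting the gain (100 per arm, 0.40 SD, equal effects).** From 1% to Bonferroni over three: 66.8 − 60.0 = 6.8 points, the excess strictness. From Bonferroni to Holm on the same contrasts: 74.5 − 66.8 = 7.7 points, the step-down gain.

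**6. Detectable effect at 0.05/3.** 100 per arm: (2.394 + 0.842) × 0.1414 = 0.458 (t-test 0.461). 70 per arm, with √(2/70) = 0.1690: 0.547 (t-test 0.553). At 1% the t-test values are 0.487 and 0.585.

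**The case against.** A reader might infer that the plan's 1% is Tukey over all six pairs of visits, and that the primary test therefore loses 7 to 15 points of power for nothing. The documents do not support that, for four reasons.

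- No passage derives 1% from Tukey or mentions six pairs. The power text justifies it by change at the post-intervention time points, which are baseline-referenced comparisons. A numerical match does not show the origin.
- The 1% appears only in the power text. The analysis text sets no such threshold, and Bonferroni over three contrasts satisfies it. On that reading 0.49 is merely a cautious planning figure and no power is lost to unneeded comparisons.
- The plan's first test is the group-by-time interaction. At 5%, with 0.40 SD at all visits, correlation 0.5 and 100 per arm, its 3-df test has 84.0% power, which the post-hoc adjustment does not change.
- The upper figure mixes excess strictness with the gain of a step-down method over a valid single-step one, and it needs equal effects at every visit.

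All four stand. It can also be said that comparisons among T2 to T4 have a use, since the time course informs the later growth models; that use is served if they are descriptive. Finally, several primary measures go unadjusted, so strictness across visits may look prudent. But a rule within one outcome does not control error across outcomes, and an undefined rule controls neither.

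**Conclusion.** The under-specification is real: three contrasts are hypothesised, two methods are offered, no family is stated, and the planning level does not match three contrasts. It concerns the visit-specific post-hoc contrasts only.

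At 0.40 SD and 100 per arm, moving from 1% (or all-pairs Tukey) to Holm over three gains about 7 points if the effect is at one visit and about 14.5 if it is equal at all three. About 7 points of this is excess strictness, or none if Bonferroni over three was intended. At 0.52 SD the gain is about 3.5 to 8 points. On the plan's own scale the adjusted detectable effect moves from 0.49 to 0.46.

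These figures assume correlation 0.5 between contrasts, equal arms, independent men, and that significance at any visit may be claimed. Treatment is delivered in groups, so positive correlation within groups would lower the power figures, and Holm holds 5% only if the model's p-values are valid. If significance at all three visits were required, no visit adjustment would be needed; the plan does not state such a rule.

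**What to change.** In To Test Exploratory Hypotheses, replace the Tukey-or-Bonferroni sentence with: *For each outcome, the three between-arm contrasts T1 to T2, T1 to T3 and T1 to T4 are tested with the Holm procedure at two-sided 5%. Comparisons among T2, T3 and T4 are descriptive.*

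In Power Analyses, restate the adjusted level as 0.05/3 and the detectable effect as 0.46 at 100 per arm (0.55 at 70 per arm).

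The cost is two sentences and one restated figure, with no new data. Holm is never less powerful than Bonferroni and keeps the same 5% family-wise limit within an outcome. Its small drawback is the lack of a simple matching confidence interval, so report Bonferroni three-contrast simultaneous intervals beside the Holm p-values.
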